### **2.5.6 Procedures to assess efficacy**

Patients are brought back to clinic for evaluation every 2 weeks. They will fill out a questionnaire reviewing their symptoms, fetal biometry will be performed, and the cervical length will be measured by transvaginal ultrasound. A physical exam (including a sterile speculum exam) will search for cervical and vaginal infections if patients are symptomatic. This information is recorded on the web-based case report form (CRF) built and stored by REDCap ([www.project-redcap.org](http://www.project-redcap.org)).

**2.5.7 Procedures to assess safety**

Patients are brought back to clinic for evaluation every 2 weeks. They will fill out a questionnaire reviewing their symptoms, fetal biometry will be performed, and the cervical length will be measured by transvaginal ultrasound. A physical exam (including a sterile speculum exam) will search for cervical and vaginal infections if patients are symptomatic. This information is recorded on the REDCap CRF.

**2.5.8 Schedule of study visits**

Schedule of Events for Pessary group +	Screening Visit	Study Visits									
	Visit 1, Day 0	Visit 2, Day 7*	Visit 3, Day 14	Visit 4, Day 28	Visit 5, Day 42	Visit 6, Day 56	Visit 7, day 70	Visit 8, Day 84	Visit 9, Day 98	Visit 10, Day 112	
Informed consent	X										
Medical history, demographics, and general health	X	X	X	X	X	X	X	X	X	X	
Review of current medications	X										
Vital signs	X	X	X	X	X	X	X	X	X	X	
Physical Exam	X	X	X	X	X	X	X	X	X	X	
Fetal biometry	X			X		X		X		X	
TVCL	X	X	X	X	X	X	X	X	X	X	

+ assume enrollment at 20 weeks  
\* if needed

Schedule of Events for Non-Pessary group +	Screening Visit	Study Visits									
	Visit 1, Day 0	Visit 2, D 7*	Visit 3, D 14	Visit 4, D 21*	Visit 5, D 28	Visit 6, D 42	Visit 7, D 56	Visit 8, D 70	Visit 9, D 84	Visit 10 D 98	Visit 11, D 112
Informed consent	X										
Medical history, demographics, and general health	X	X	X	X	X	X	X	X	X	X	X
Review of current medications	X										
Vital signs	X	X	X	X	X	X	X	X	X	X	X
Physical Exam	X	X	X	X	X	X	X	X	X	X	X
Fetal biometry	X				X		X		X		X
TVCL	X	X	X	X	X	X	X	X	X	X	X

+ assume enrollment at 20 weeks

\* if needed

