## **2.4 Subject selection**

### **2.4.1 General characteristics of the proposed subject population(s)**

The patients enrolled into this study are < 23 weeks 0 days pregnant and will have a cervical length < 25 mm detected by transvaginal ultrasound performed during universal screening at each institution participating in this trial. These patients are seeking care at a tertiary care center, and in general have a higher risk profile compared to the community due to presence of maternal disease such as diabetes or hypertension or obstetric history such as prior preterm birth.

The Arabin pessary is designed to reduce preterm birth in pregnant patients with a short cervix. The suggested patients for this clinical trial exactly match the type of patients treated by the Arabin pessary.

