### **2.5.2 Study treatment or diagnostic product procedures**

The treatment proposed in this study is the placement of the Arabin pessary around the cervix. This device currently does not have FDA approval. The company which manufactures the device in Europe has applied for FDA license. A consultant report by NAMSA which describes the device, classification, safety, toxicity, and testing is included in this application.

Patients in the experimental arm will have the Arabin pessary placed at time of enrollment. First, they are assessed for uterine contractions by tocodynamometer. To repeat, if symptoms of genital infection are present, the investigator will perform a sterile speculum exam and a wet mount and cervical cultures for gonorrhea/chlamydia will be obtained. Any symptomatic infections are treated, and the pessary insertion is delayed a week. Any infections resulting after pessary insertion will also be treated. When the pessary is placed, a sterile vaginal examination gel (non-antibiotic) will be used. Once the pessary is placed, patients will return to clinic every 2 weeks for an evaluation. A questionnaire will be filled out for symptoms, and a speculum exam performed to search for infections if the patient is symptomatic. Fetal biometry will be performed monthly, and a transvaginal cervical length will be measured every 2 weeks. The pessary will be removed if there are signs of tissue erosion of the cervix or vagina, intractable pain, or labor. Otherwise, the pessary is removed at 37 weeks.

The control arm will be followed with serial transvaginal ultrasounds to measure cervical length. If the length decreases to less than 20 mm, then vaginal progesterone 200 mg will be prescribed from a local pharmacy. If the cervical length continues to shorten such that membranes are visible at the os, then an emergent cerclage will be offered. Treatments will not be offered after 24 weeks gestation. Similar to the experimental group, patients will return to clinic every 2 weeks for an evaluation. A questionnaire will be filled out for symptoms, and a speculum exam performed to search for infections if the patient is symptomatic. Fetal biometry will be performed monthly, and a transvaginal cervical length will be measured every 2 weeks.

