### **2.5.4 Treatment adherence**

Patients are asked to return to clinic at frequent intervals for an evaluation that includes history, transvaginal ultrasounds, and physical exam if needed. The pessary patients will return every 2 weeks after the pessary is placed. The control patients will have a weekly transvaginal ultrasound up to 24 weeks, then a clinic visit every 2 weeks.

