### **2.5.5 Withdrawal of subjects due to non-compliance**

An intent-to-treat analysis will be used for analyzing study results. In the pessary group, if a patient removes the pessary, their outcomes will still be analyzed in the pessary group. In the control group, if patients do not use vaginal progesterone, their results are still analyzed in the control group. Patients who receive emergency cerclages are 100% compliant.

If patients do not return for their clinic visits or their delivery information is lost, their data cannot be analyzed. The investigators will call a minimum of 2 times, separated by a week, to ensure follow up. If unsuccessful, a letter will be mailed to the address of record requesting follow up. With regards to the primary outcome of preterm delivery, they will be assumed as having delivered the pregnancy at the gestational age they were lost to follow up.

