## **2.6 Study outcome evaluations**

### **2.6.1 Study endpoints**

These are listed in sections 1.4.1 and 1.4.2. To repeat, the primary outcome is a preterm delivery less than 37 weeks 0 days.

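### The only contact fixed at 37 weeks is pessary removal, so under the loss rule some late-lost controls can be scored preterm while comparable pessary women are scored term

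*Combined protocol and SAP*

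**What the plan says.** - **Endpoint.** Section 2.6.1: "the primary outcome is a preterm delivery less than 37 weeks 0 days".
- **Visit tables.** In section 2.5.8 the pessary table ends at "Visit 10, Day 112". The control table ends on the same study day, as its Visit 11. Both carry the footnote "assume enrollment at 20 weeks". Neither lists a 37-week visit.
- **Entry.** Section 2.4.1: "The patients enrolled into this study are < 23 weeks 0 days pregnant". Twenty weeks is therefore an illustration and not a fixed entry age.
- **The 37-week contact.** Section 2.5.2, pessary arm only: "Otherwise, the pessary is removed at 37 weeks". Earlier removal is possible: "The pessary will be removed if there are signs of tissue erosion of the cervix or vagina, intractable pain, or labor". No control contact is tied to 37 weeks.
- **Visits in the text.** Section 2.5.4: "The control patients will have a weekly transvaginal ultrasound up to 24 weeks, then a clinic visit every 2 weeks". Section 2.5.2 also gives fortnightly visits in both arms. Neither section says when they end.
- **Loss rule.** Section 2.5.5, for the primary outcome: "they will be assumed as having delivered the pregnancy at the gestational age they were lost to follow up". Section 2.6.3 repeats the rule, adds a sensitivity analysis without the incomplete cases, and makes success depend on significance and on incomplete data not exceeding 10%.

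**The concern.** For a lost woman, the loss rule turns the date of loss into the primary outcome. Whether she counts as preterm then depends on when the protocol last arranged to see her, and that differs by arm just at the cut-off. The pessary arm has a stated reason to be seen at 37 weeks, and the control arm has none.

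The error can only move the comparison towards the pessary, and the trial is open-label. It also differs from a general objection to the loss rule. With the same last contact in both arms, the rule would treat late losses alike. The asymmetry arises because the contact pattern and the rule act together.

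**Working it through.** **The plan's own sample size first.** Inputs from section 2.6.2: 30% against 15%, two-sided 0.05, power 80%, pooled variance. With mean rate 0.225:

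n per arm = [1.96 × √(2 × 0.225 × 0.775) + 0.8416 × √(0.30 × 0.70 + 0.15 × 0.85)]² / 0.15² = (1.157 + 0.489)² / 0.0225 ≈ 120.5, so 121 per arm and 242 in total.

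This matches the plan. 242 / 0.95 = 254.7, so 255; the plan enrols 256, or 128 per arm. The sample size is not in question here.

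**Timing.** 37w0d is 259 days.

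| Entry | Day 112 falls at | At or past 37w0d? |
|---|---|---|
| 18w0d | 34w0d | no |
| 20w0d | 140 + 112 = 252 days = 36w0d | no |
| 20w6d | 36w6d | no |
| 21w0d | 147 + 112 = 259 days = 37w0d | yes |
| 22w6d | 38w6d | yes |

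If fortnightly visits continue past the table, the next one after entry at 20w0d is day 126: 140 + 126 = 266 days = 38w0d. Controls would still have no contact at 37 weeks.

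**How lost women are scored (entry before 21w0d, date of loss read as last contact).**

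| Woman | Scored |
|---|---|
| Control lost after the day-112 visit, no later contact | preterm |
| Pessary woman lost between day 112 and removal | preterm |
| Pessary removed early, no contact at or after 37w0d | preterm |
| Pessary woman seen for removal at 37w0d or later, then lost | term |

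Only the last row differs from the controls.

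**Size.** Expected loss is 0.05 × 128 = 6.4, about 6 per arm. The timing of losses is not in the documents, so the net number k of misclassified controls is an assumption, taken here from 0 to 6. The true rate is set at 30% in both arms. Control events are Bin(128, 0.30) + k and pessary events are Bin(128, 0.30). The test is the pooled z-test, and the probability that z > 1.96 in favour of the pessary is found by exact enumeration.

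| k | Shift in control rate (k/128) | Chance of a false result favouring the pessary |
|---|---|---|
| 0 | 0 | 2.5% |
| 1 | 0.8 points | 3.4% |
| 2 | 1.6 points | 4.5% |
| 3 | 2.3 points | 5.9% |
| 6 | 4.7 points | 12.0% |

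If 6 controls and 3 pessary women are scored preterm in this way, the chance is 5.4%.

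**Cross-check with expected rates.** Here the 5% lost are taken out of the women with known outcome, and a normal approximation is used.

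- All losses late, every lost pessary woman seen at removal: control 0.95 × 0.30 + 0.05 = 33.5%, pessary 0.95 × 0.30 = 28.5%. The spurious difference is 5.0 points and the two-sided type I error is 0.139 (0.136 of it favouring the pessary). This is slightly above 12% because it uses 6.4 women rather than 6, and an approximation.
- Half late, all of those seen: 33.5% against 31.0%, 2.5 points, type I error 0.071.
- A quarter late, half of those seen: 33.5% against 32.9%, 0.6 points, type I error 0.051.

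If late losses are scored alike in both arms, the difference is 0 and the type I error is 0.050.

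**The case against.** The strongest reply has five parts.

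1. **Control visits are not said to stop at 36 weeks.** This stands. The text gives fortnightly visits without an end date, and the synopsis puts participation at about seven months. A reader might infer from the tables that controls have no contact at or after 37w0d; the documents do not support that. However, for entry at 20w0d the next visit is at 38w0d, so a gap at 37 weeks remains. For entry at 19w0d, continued visits would reach 37w0d exactly (133 + 126 = 259 days) and close it.
2. **The date of loss is undefined.** This also stands. If a control seen at 36w0d is dated as lost at a missed 38w0d visit, she is scored term. Scoring her at her last contact is one reading of sections 2.5.5 and 2.6.3, though a natural one.
3. **Few women can be affected.** True. Delivery outcomes come from hospital charts, including those of other hospitals with consent, and section 2.5.5 provides at least two calls and then a letter. Only women whose delivery record is still missing matter, and only those who entered before 21w0d. The plan nevertheless expects about 5% loss.
4. **The loss rule is the root cause.** Partly true: without it there would be no such bias. With it, the unequal contact pattern is what makes the error differ by arm.
5. **The sensitivity analysis omits these women.** It may reveal the bias, but the success rule in section 2.6.3 does not depend on its result, and 5% loss passes the 10% limit.

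A reader might also infer that late-lost controls are scored preterm and late-lost pessary women are not, as a general rule. That is too broad: pessary women lost before removal, or after early removal with no later contact, are scored like controls.

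**Conclusion.** The concern holds in a limited form. As written, the plan can misclassify the primary endpoint in favour of the pessary for women who entered before 21w0d and are lost around 36 to 38 weeks without a delivery record. For entry at 21w0d or later, the last tabulated visit is already at or past 37w0d in both arms and the problem disappears.

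At the stated 5% loss, the chance of a false result favouring the pessary lies between the nominal 2.5% and a ceiling of about 12%. The ceiling requires every expected loss to fall late and every lost pessary woman to have attended removal first. A reader might take 12% as the expected size, but the documents give neither the timing of losses nor attendance at removal, and milder assumptions leave the error close to nominal.

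The range rests on 128 per arm, a 30% rate in both arms and last contact as the date of loss. It concerns the plan only: the cover letter states that the trial closed with 7 women enrolled and no tests run.

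**What to change.** 1. Add to both tables in section 2.5.8 the same outcome check at 37w0d by gestational age rather than study day: a call or chart check recording delivered or undelivered.
2. State in sections 2.5.5 and 2.6.3 that the date of loss is taken from these common checks in both arms, and not from the pessary-removal visit.
3. Reconcile sections 2.5.2, 2.5.4 and 2.5.8 on when visits end in each arm.

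This changes outcome ascertainment only and leaves clinical management as it is. The cost is one call or chart check per woman and some wording. One consequence should be accepted openly: a pessary woman seen at removal but missed by the common check would be scored without using the removal visit, so the check should be pursued equally hard in both arms to keep such cases rare.

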## **2.6 Study outcome evaluations**

### **2.6.1 Study endpoints**

These are listed in sections 1.4.1 and 1.4.2. To repeat, the primary outcome is a preterm delivery less than 37 weeks 0 days.

### **2.6.2 Sample size determination**

Based on KUMC hospital data, the number of preterm births < 37 weeks 0 days gestation in patients with short cervixes (< 25 mm) is 30%. In order to detect a reduction in half to 15%, a sample size of 242 will be required to have power of 80% using a two-sided z-test assuming pooled variances. Level of significance is set at 0.05.

Based on records of patients currently treated for short cervixes here at KUMC over the past year, we experience about a 5% loss to follow up rate. Our sample size determination requires 242 subjects for analysis. We plan to enroll a total of 256 patients. We will use an intent-to-treat principle for analyzing the outcomes of the trial. All enrolled patients will provide informed consent for study participation.

### **2.6.3 Outcome data and data analysis**

When patients are admitted to the hospital for delivery of the fetus, the research team will record the information listed on the REDCap CRF. Both the mother and newborn hospital charts will be reviewed for the primary and secondary outcomes listed in sections 1.4.1 and 1.4.2. If patients deliver at another hospital, those records will be obtained with the patient's consent.

De-identified data from each institution will be stored on the REDCap website. That data will be downloaded into either Excel or SAS format for analysis. This file will be stored in the folder of [name] MD, on the network server named "Sydney". This drive is password protected. Only members of the research team will be given access to the stored data.

The primary endpoint and the categorical outcomes that are part of the secondary endpoints will be reported using frequency counts and proportions. For the secondary endpoints that are continuous variables, summary statistics such as mean and standard deviation, or median and inter-quartile range will be reported based on whether the assumption of normality is justified. A chi-square test (or a Fisher's exact test) will be used to perform statistical comparison of proportions across the two groups. Likewise, comparisons for continuous outcomes will be done using a two-sample t-test (or Wilcoxon Rank Sum test) as will be deemed necessary. For gestational age, we will also compare the Kaplan Meier survival curves of the two groups (control and pessary) using the logrank test. Level of significance for all statistical tests will be set at 0.05.

As mentioned before, subjects lost to follow up will have the gestational age at delivery set at the point data was lost. An intent to treat analysis will then be performed. A sensitivity analysis will be conducted by omitting the incomplete data and recalculating the differences between the pessary and control groups. The changes in results will then be compared.

The Arabin pessary will be considered a success if the following conditions are met: 1) a statistically significant reduction of preterm birth is found in the group treated with the Arabin pessary, 2) the number of patients with incomplete data does not exceed 10%. If a statistically significant difference is observed, but missing data is equal or greater than 10%, then additional study with a larger sample size is warranted.

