PLANNED INTERIM ANALYSES	The data will be reviewed every 6 months by the designated medical monitor for the study, [name] MD (neonatologist). The medical monitor is specifically chosen outside of the department of OBGYN to allow for objectivity. Adverse events which would requires immediate suspension of study for review would include an excess of 1 maternal death, 1 maternal ICU admission for sepsis, or 2 perinatal deaths in the pessary group. Unanticipated adverse events will be reported immediately to the Human Subjects Committee (HSC) and the FDA, and its recommendations for temporary cessation or continuation of the study will be followed. If an excess of 4 perinatal deaths occur in the pessary group, the study should be concluded.

STATISTICS Primary Analysis Plan	
The Research hypothesis is that proportion of preterm deliveries before 37 weeks 0 days gestation is reduced in the pessary group as compared to the control group. The primary endpoint and the categorical outcomes that are part of the secondary endpoints will be reported using frequency counts and proportions. For the secondary endpoints that are continuous variables, summary statistics such as mean and standard deviation, or median and inter-quartile range will be reported based on whether the assumption of normality is justified. A chi-square test (or a Fisher's exact test) will be used to perform statistical comparison of proportions across the two groups. Likewise, comparisons for continuous outcomes will be done using a two-sample t-test (or Wilcoxon Rank Sum test) as will be deemed necessary. For gestational age, we will also compare the Kaplan Meier survival curves of the two groups (control and pessary) using the logrank test. Level of significance for all statistical tests will be set at 0.05.

Rationale for Number of Subjects	
Based on KUMC and MUSC hospital data, the proportion of preterm births before 37 weeks 0 days gestation in patients with short cervixes is 30%. In order to detect a reduction in half to 15%, a sample size of 242 will be required to have power of 80% using a two-sided z-test assuming pooled variances. Level of significance is set at 0.05. We anticipate a loss to follow up rate of 5%. We expect to enroll 256 subjects.

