#### 1.4.2 Secondary Objectives

- Neonatal composite morbidity – fetal or neonatal death, respiratory distress syndrome (RDS), chronic lung disease, periventricular lucency, periventricular leukomalacia, intraventricular hemorrhage grade 3 or 4, necrotizing enterocolitis, early-onset-culture-proven sepsis
- Neonatal length of stay
- Neonatal NICU admission
- Total NICU days
- Duration of ventilator support
- retinopathy of prematurity (ROP) requiring treatment
- birthweight < 1500g and < 2500g
- preterm birth < 34 weeks
- gestational age at delivery
- use of tocolysis
- use of antenatal steroids
- chorioamnionitis
- vaginal bleeding
- preterm premature rupture of membranes
- cesarean delivery

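### The median/IQR rule would show nothing for ventilator days, and for NICU days would give no estimate of days saved or added

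*Combined protocol and SAP*

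**What the plan says.** Section 1.4.2 lists "Total NICU days" and "Duration of ventilator support" among the secondary endpoints. NICU admission and neonatal length of stay are listed separately. Whether an infant was ventilated at all is not an endpoint.

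Section 2.6.3 has one descriptive rule for every continuous secondary endpoint: mean and SD, or "median and inter-quartile range will be reported based on whether the assumption of normality is justified". The Statistics row of the synopsis adds that "comparisons for continuous outcomes will be done using a two-sample t-test (or Wilcoxon Rank Sum test) as will be deemed necessary". No between-arm difference in days and no confidence interval is specified.

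The documents do not say whether days are counted over all infants or only over those admitted or ventilated. They give no NICU admission or ventilation rate. The intent-to-treat statements in 2.4.2, 2.6.2 and 2.6.3 point to all infants.

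**The concern.** Counted over all infants, both variables have a large spike at zero and a long right tail. Normality will not be judged to hold, so the rule leads to median and IQR with a Wilcoxon test. A median is uninformative once more than half of the infants have zero days, and an upper quartile is uninformative once more than three quarters do.

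At stake is the neonatal-morbidity objective. NICU and ventilator days are there to measure burden in days. A report that gives only quartiles may not be able to say how many days the pessary saves or adds.

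**Working it through.** **Inputs from the documents.** Section 2.6.2 says that "the number of preterm births < 37 weeks 0 days gestation in patients with short cervixes (< 25 mm) is 30" per cent. The effect sought is given as "In order to detect a reduction in half to 15" per cent, with "power of 80% using a two-sided z-test assuming pooled variances", and "Level of significance is set at 0.05".

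**The plan's own figure.** With mean proportion 0.225,

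n per arm = [1.960 × √(2 × 0.225 × 0.775) + 0.842 × √(0.30 × 0.70 + 0.15 × 0.85)]² / 0.15² = 120.5, rounded up to 121.

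The total is 242, as stated, so 121 per arm is used below.

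**When is the NICU median above 0?** Let a be the NICU admission rate of preterm infants and t that of term infants. The share with any NICU days is 0.30a + 0.70t in control and 0.15a + 0.85t in the pessary arm. A median above 0 needs a share above 0.50. With a = 1, the case most favourable to a non-zero median:

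- control: t > (0.50 − 0.30)/0.70 = 28.6%
- pessary: t > (0.50 − 0.15)/0.85 = 41.2%

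With a = 0.6 the thresholds rise to (0.50 − 0.18)/0.70 = 45.7% and (0.50 − 0.09)/0.85 = 48.2%.

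**Sampling variation.** With 121 infants the sample median exceeds 0 only if at least 61 have NICU days. The documents give no admission rates, so I assume ranges: a from 40% to 100%, t from 0% to 20%. Any NICU days then occur in 12-44% of control and 6-32% of pessary infants. By the exact binomial, the chance of a control median above 0 is under 0.4% throughout, except 9% at the corner a = 100%, t = 20%.

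**Upper quartile.** It exceeds 0 only if more than 25% have days. In the pessary arm with a = 1 this needs t > (0.25 − 0.15)/0.85 = 11.8%.

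**Simulation.** 121 infants per arm. Stays among affected infants are lognormal, rounded up to whole days, with assumed mean 20 days (NICU) or 6 days (ventilator) and log-SD 1.0. Where a range is shown, log-SD runs from 0.8 to 1.2. All rates and stays in the table are assumptions, control v pessary.

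| Scenario | Any days | Mean days per infant | Both medians 0 | Typical upper quartile | Wilcoxon power |
|---|---|---|---|---|---|
| NICU: all preterm, no term admitted | 30% v 15% | 6.2 v 3.1 | 100% | 3-7 v 0 | 78-81% |
| NICU: all preterm, 10% of term | 37% v 23.5% | 7.6 v 4.8 | 99.9% | 8 v 0 | 60% |
| NICU: 60% of preterm, 5% of term | 21.5% v 13.25% | 4.5 v 2.7 | 100% | 0 v 0 | 39% |
| NICU: duration only, mean stay 20 v 10 | 30% v 30% | 6.2 v 3.1 | 100% | 5 v 3 | 8-11% |
| Ventilator, lower | 10% v 5% | 0.6 v 0.3 | 100% | 0 v 0 | 31% |
| Ventilator, higher | 20% v 10% | 1.3 v 0.65 | 100% | 0 v 0 | 58% |

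In both ventilator rows the true burden is halved, and the typical report is 0 (IQR 0-0) in each arm.

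**Would a test of means be better?** In the first row, Welch's t-test (as a proxy for a permutation test of the mean difference) has power of about 33-54%, against 78-81% for the Wilcoxon. In the duration-only row a t-test has about 45%, against 9% for the Wilcoxon, both at log-SD 1.0. Swapping the test would trade one weakness for another.

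**The case against.** Several objections carry weight.

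- **The denominator is not stated.** If only admitted or ventilated infants are counted, the medians are not 0. This stands as a limit on the point. But that reading compares subsets formed after randomisation and sits poorly with intent-to-treat, so the plan should say which is meant.
- **The rule is loose.** Section 2.6.3 introduces its summaries as examples and leaves the choice of test open, so means are not excluded. That is true, but none is committed to, and in an open-label trial the choice should not wait for the data.
- **NICU days are not lost from view.** A reader might infer that they would read 0 v 0 whatever the pessary does, or that the trial could not detect a halving. The documents do not support this. The IQR is reported as well, the Wilcoxon test has about 80% power at 30% v 15% with any days, and NICU admission is reported as a proportion. Neonatal length of stay is a further endpoint in days.
- **The weight is small.** Neither endpoint enters the success criterion in 2.6.3 or the sample size, and median with IQR is a conventional summary for skewed stays. This stands and limits the severity.

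The objections do not answer the ventilator case, where no proportion accompanies the days. Nor do they supply an estimate of the days effect for either endpoint.

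**Conclusion.** The point holds, and it is minor. Counted over all infants, both medians would be 0 unless more than about 29% (control) and 41% (pessary) of term infants had NICU days. Those thresholds rest on the plan's 30% v 15% and the generous assumption that every preterm infant is admitted.

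It is strongest for ventilator days. At assumed ventilation of 10-20% v 5-10%, the descriptive report would typically show nothing, although a Wilcoxon p-value would still be produced. For NICU days a change in incidence would remain visible, at least through the admission proportion. What is missing is an estimate in days. Power for a change in duration alone is also low, about 8-11% with 30% admitted in both arms and assumed mean stays of 20 v 10 days.

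The primary endpoint and the sample size are unaffected. The cover letter says that the trial closed with 7 subjects and that no tests were run, so this concerns the plan as written and not any reported result.

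**What to change.** In 2.6.3, keep the Wilcoxon test and add for NICU days and ventilator days:

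- the denominator: all infants with known outcome, zeros included. The loss-to-follow-up rule in 2.6.3 sets only gestational age at delivery, so days for infants lost are unknown, and their number should be given by arm
- mean days per infant by arm, and the between-arm difference with a bootstrap 95% CI
- the proportion with any ventilation, to match the existing NICU-admission endpoint
- fetal and neonatal deaths by arm alongside, with a sensitivity analysis that ranks deaths as the worst outcome, so that an early death is not read as fewer days.

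The cost is a few sentences of SAP text and a few lines of code. The downside is that means are sensitive to a few long stays, so the intervals will be wide.

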## **2.3 Study design**

### **2.3.1 General study design**

This study is a randomized controlled trial. It is not blinded to either investigator or patient.

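### Read literally, 2.6.3 counts women lost to follow-up as deliveries in the secondary log-rank test, and no section gives a censoring rule; this distorts the test's error rate only if loss differs between arms

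*Combined protocol and SAP*

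**What the plan says.** Gestational age at delivery is a listed secondary endpoint (1.4.2). Section 2.6.3 and the synopsis both plan the time-to-event comparison: "For gestational age, we will also compare the Kaplan Meier survival curves of the two groups (control and pessary) using the logrank test". All tests use a 0.05 level.

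Two sections deal with women lost to follow-up, and they do not agree.

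- Section 2.5.5: "If patients do not return for their clinic visits or their delivery information is lost, their data cannot be analyzed". It then makes an exception: "With regards to the primary outcome of preterm delivery, they will be assumed as having delivered the pregnancy at the gestational age" at which they were lost. The exception is worded for the primary outcome only.
- Section 2.6.3: "subjects lost to follow up will have the gestational age at delivery set at the point data was lost", followed by the intent-to-treat analysis. Here nothing limits the rule to the primary outcome, and the variable it fixes is the one the log-rank test uses.

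Section 2.6.3 adds: "A sensitivity analysis will be conducted by omitting the incomplete data and recalculating the differences between the pessary and control groups". No section says who is censored, or when, in the Kaplan-Meier analysis. On the amount of loss, 2.6.2 says only that "we experience about a 5% loss to follow up rate". No split by arm is given.

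**The concern.** Kaplan-Meier and log-rank methods can use a woman's follow-up to the day she is lost without recording an event. Under the literal rule in 2.6.3, a woman last seen pregnant at 26 weeks becomes a delivery at 26 weeks. If one arm loses more women, that arm gains early deliveries that nobody observed, and the test can show a difference in gestational age where none exists.

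Unequal loss is possible. Of the design, 2.3.1 says: "It is not blinded to either investigator or patient". The visit plans also differ somewhat: "The control patients will have a weekly transvaginal ultrasound up to 24 weeks, then a clinic visit every 2 weeks" (2.5.4).

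A secondary result tested at 0.05 is at stake, and so is reproducibility. One analyst following 2.5.5 and another following 2.6.3 could report different log-rank results from the same data.

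**Working it through.** **Plan's own figures.** Inputs from 2.6.2 and 2.4.2: 30% against 15%, two-sided 0.05, 80% power, pooled z-test, 1:1 allocation.

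n per arm = [1.96√(2 × 0.225 × 0.775) + 0.842√(0.30 × 0.70 + 0.15 × 0.85)]² / 0.15² ≈ 120.5, so 121 per arm and 242 in total, as stated. Then 242 / 0.95 = 254.7, or 255; the plan enrols 256 (128 per arm). The documents give no error rate for the log-rank test, so it has to be derived.

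**Hand approximation, no true effect, all losses counted as deliveries.** The log-rank numerator for one arm is the sum over its women of 1 − H(x), where H is the pooled cumulative hazard at the recorded time x. The average score is zero. A woman lost early has H near 0 and adds about 1. With 256 events the standard deviation is about √(256/4) = 8.

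- 7.5%/2.5%: excess losses 128 × (0.075 − 0.05) = 3.2; shift 3.2/8 = 0.40. Rejection = P(Z > 1.56) + P(Z < −2.36) = 5.9% + 0.9%, about 6.9% before rounding.
- 9%/1%: 128 × 0.04 = 5.12; shift 0.64. Rejection = 9.3% + 0.5% = 9.8%.
- 6%/4%: 128 × 0.01 = 1.28; shift 0.16. Rejection = 3.6% + 1.7% = 5.3%.

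**Simulation.** 20,000 trials per row, 128 per arm, 30% preterm in both arms, whole days, Monte Carlo standard error about 0.15 points at 5%. Assumptions: preterm day 161 + 98 × Beta(2.5, 1.2); term day 259 + Normal(14, 7) truncated to 0–35; loss unrelated to outcome and uniform from 22 weeks to the earlier of 36 weeks and delivery. Every split is an assumption.

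| Loss, control/pessary | Counted as delivery | Censored at loss | Omitted |
|---|---|---|---|
| 5%/5% | 4.8% | 4.8% | 4.8% |
| 6%/4% | 5.4% | 5.2% | 5.1% |
| 7.5%/2.5% | 6.9% | 5.2% | 5.2% |
| 2.5%/7.5% | 7.0% | 5.2% | 5.2% |
| 9%/1% | 9.9% | 5.0% | 5.1% |
| 15%/5% (twice the planned loss) | 13.4% | 5.2% | 5.2% |

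At 7.5%/2.5%, 5.9 of the 6.9 points favour the pessary. With the split reversed, only 0.9 of the 7.0 points do.

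**Timing of loss.** A second set of simulations crossed three delivery distributions with three loss timings (8,000 trials per cell, with further 10,000-trial runs for uniform timing), again counting losses as deliveries.

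| Loss timing | 7.5%/2.5% | 9%/1% |
|---|---|---|
| Early | 7.3–7.5% | 10.6–10.7% |
| Spread over follow-up | 6.5–7.3% | 8.8–9.9% |
| Late | 5.9–6.5% | 7.7–8.8% |

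Equal 5% loss gave 4.8–5.3%, and censoring gave 4.8–5.7% throughout. Late loss matters less because H is no longer near 0.

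**Loss related to outcome** (assumed: 60% of lost women truly preterm).

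| Loss, control/pessary | Counted as delivery | Censored | Omitted |
|---|---|---|---|
| 7.5%/2.5% | 6.1% | 5.6% | 5.5% |
| 9%/1% | 7.1% | 6.5% | 6.1% |
| 15%/5% | 8.0% | 6.9% | 6.5% |

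**Power at equal 5% loss, 15% against 30% preterm.** Counted as delivery against censored: 28.1% and 29.2% in a preterm/term mixture model, 50.4% and 51.8% in a Weibull model. The cost is about 1 point.

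**Could chance alone give these splits?** 5% of 256 is about 13 losses. If each is equally likely in either arm, 10 against 3 (about 7.5%/2.5%) or worse has two-sided probability 2 × (286 + 78 + 13 + 1)/8192 = 0.09. For 12 against 1 (about 9%/1%) it is 2 × (13 + 1)/8192 = 0.003.

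**The case against.** The strongest reply is that the plan may not mean this at all. The rule in 2.6.3 refers back to 2.5.5, which confines assumed delivery to the primary outcome, and choosing Kaplan-Meier suggests that censoring was intended. This stands in part. The secure defect is an unreconciled difference between two sections and a missing censoring rule. The plain wording of 2.6.3 still favours counting losses as deliveries.

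Second, the imbalance has little support in the documents. A reader might infer from the weekly control scans that controls would drop out more, and hence that the rule favours the pessary. The documents do not show this. Section 2.5.2 has controls returning every two weeks like the pessary arm. In 2.5.8 both arms have an optional Day 7 visit, and controls add only an optional Day 21 visit. The direction of any imbalance is unknown, and the 9%/1% split would need a real difference in loss between arms. Repeat calls and a letter (2.5.5), and records from outside hospitals (2.6.3), should also limit loss.

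Third, the planned analysis omitting incomplete data brings the rate back to about 5% if loss is unrelated to outcome. That is correct. However, 2.6.3 says only that the change in results will be compared, not which result stands.

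**Conclusion.** The point holds as a minor to moderate one. Read literally, the log-rank analysis counts lost women as deliveries; 2.5.5 points the other way; no censoring rule settles it. With equal loss the false-positive rate is nominal, although about 1 point of power is lost and both curves shift earlier. With assumed splits from 7.5%/2.5% to 9%/1% in either direction, the rate is about 6% to 10%, depending on when loss occurs and whether it relates to outcome. Nearly all the excess favours the arm with less loss. At 6%/4% it is negligible.

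Two stronger readings are not supported. One is that the plan's log-rank test has a 7% to 10% error rate: that range needs an undocumented imbalance and loss that is neither late nor outcome-related. The other is that the trial's conclusion is at risk through this test: the success rule in 2.6.3 rests on preterm birth and the amount of incomplete data. The cover letter also reports 7 women enrolled and no tests run, so this concerns the plan and not a result.

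**What to change.** Reconcile 2.5.5 with 2.6.3. In 2.6.3 and the synopsis, state that for the Kaplan-Meier curves and log-rank test women lost to follow-up are censored at the last date known to be pregnant. Keep the delivery-at-loss and omit-incomplete versions as sensitivity analyses.

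The cost is a sentence or so in each place and no new data. The two-weekly visits in 2.5.6 supply the date, and censoring at the last such visit gave the same 4.8% to 5.2% as censoring at the exact day of loss.

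The downside is that censoring assumes loss is unrelated to delivery timing. If lost women are more often preterm, the rate stays at about 5% to 7%, and the remaining errors favour whichever arm loses more. If that is the pessary arm, false positives favouring the pessary were about 4% to 6% with censoring, against about 1% under the literal rule. This is why the delivery-at-loss version should be kept alongside.

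The edit does not repair the other tests that use the same loss rule. At 7.5%/2.5% and 9%/1% the rates were 9.1% and 15.9% for the primary chi-square test, 13.3% and 27.6% for the t-test, and 9.2% and 15.9% for the Wilcoxon test. Those need their own decision.
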